^d Subjects will attend EPV2 when they enter the long-term study. Before entering the long-term study, subjects must have been switched to BRV oral solution and be able to tolerate it. Subjects who have not been switched to BRV oral solution will not be permitted to continue into the long-term study. The timing of switching from iv to oral solution will be at the discretion of the Investigator. Subjects will continue to receive the same BRV dose administered at the end of the Evaluation Period.

^e Parent(s) or legal representative(s) will be informed about the study as early as possible and asked to sign the informed consent after the occurrence of seizures is confirmed on VEEG. Continuous consent will be ensured by meetings between the Investigator (or designee) and the subject's parent(s) or legal representative(s), during the conduct of the study.

^f To be performed on the first day of the Down-Titration Period only.

^g If the subject enters the long-term study, no study drug from N01349 will be dispensed in EPV2. If the subject does not enter the long-term study, BRV from N01349 will be administered for down-titration (only applicable to subjects from the Confirmatory Cohorts).

^h The Down-Titration steps and duration may be adjusted at the Investigator's discretion.

ⁱ Video-EEG will only apply to subjects of the Confirmatory Cohorts who complete the study after the Evaluation Period. The VEEG will be recorded for at least 1 hour on the final day of the Down-Titration Period. Additional VEEGs can be performed at any time during the Down-Titration Period at the Investigator's discretion.

^j Bayley-III assessment will be assessed for subjects continuing into the long-term study, in countries where a validated translation is available.

^k The recording of AEDs will include AEDs (BZDs and opiates) taken by the mother at the time of delivery. In addition, details regarding COVID-19 vaccination will be recorded as concomitant medication if mother was pregnant or breastfeeding when vaccinated.

^l Infusion site reactions will only be monitored for subjects receiving iv BRV. Monitoring for BRV infusion site reactions should take place during and 30 minutes after the end of the infusion.

^m Updated Medical History should be recorded at EPV2 for subjects entering the long-term study.

ⁿ Updated Medical History should be recorded for subjects not entering the long-term study.

^o Laboratory assessment (safety) only required for Unscheduled Visits performed during the BRV Extension Period.

Table 5–4: Schedule for PK Sampling (Exploratory Cohort)

Assessment	48-hour Evaluation Period					
	Time relative to the start of the most recent BRV infusion					
	Day 1			Day 2 ^a		
BRV PK samples ^c	X	X	X	X	X	X
AED PK sample		X ^d				

AED=antiepileptic drug; BRV=brivaracetam; h=hours; min=minutes; PK=pharmacokinetic(s)

Note: Blood for PK samples should be drawn from a line different to that of the BRV infusion.

^a Blood sampling is only needed on Day 2 if subjects are dosed with BRV on Day 2.

^b The first PK sample should be collected 30 to 60 minutes after the start of the BRV infusion.

^c The BRV PK sampling timepoints for the first 3 samples of the Exploratory Cohorts are as follows: 30 to 60 minutes, 2 to 4 hours, and 8 to 12 hours after the start of the most recent BRV infusion. The second set of 3 samples will be collected at the same timepoints on the second day of the 48-hour Evaluation Period.

^d The AED PK sample should be collected 3 hours after the start of the initial BRV administration.

This document cannot be used to support any marketing authorization application and any variations thereof.
PUBLIC COPY

Table 5–5: Schedule for PK Sampling (Confirmatory Cohorts)

Assessment	96-hour Evaluation Period											
	Time relative to the start of the most recent BRV infusion											
	Day 1			Day 2			Day 3			Day 4		
	30-60mi n ^a	2-4 h	8-12 h	30-60m in	2-4 h	8-12 h	30-60m in	2-4 h	8-12 h	30-60m in	2-4 h	8-12 h
BRV PK samples ^b	X	X	X	(X)	(X)	(X)	(X)	(X)	(X)	(X)	(X)	(X)
AED PK sample		X ^c										

AED=antiepileptic drug; BRV=brivaracetam; h=hours; PK=pharmacokinetic(s); min=minutes; (X)=optional for that day

Note: Blood for PK samples should be drawn from a line different to that of the BRV infusion.

^a The first PK sample will be collected 30 to 60 minutes after the start of the BRV infusion.

[figure not shown]
^b The BRV PK sampling timepoints for the first 3 samples of the Confirmatory Cohorts are as follows: 30 to 60 minutes, 2 to 4 hours, and 8 to 12 hours after the start of the most recent BRV infusion. The second set of 3 PK samples will be collected within the same timeframes as the first set on one of the following days: either Day 2 (post-24 hours), OR Day 3 (post-48 hours) OR Day 4 (post-72 hours). It is acceptable if these samples are drawn on different days.

^c The AED PK sample should be collected 3 hours after the start of the initial BRV administration.

5.3 Schematic diagrams

Figure 5–1 displays a schematic overview of the study for the Exploratory Cohort and the Screening and Evaluation Periods of this Cohort are presented in detail in Figure 5–2. Figure 5–3 displays a schematic overview of the study for the Confirmatory Cohorts and the Screening and Evaluation Periods of these Cohorts are presented in detail in Figure 5–4.

[figure not shown]
Figure 5-1: Schematic overview of the study (Exploratory Cohort)

AED=antiepileptic drug; BRV=brivaracetam

^a BRV to be administered in addition to another AED.

Figure 5–2: Screening and Evaluation Periods (Exploratory Cohort)

[figure not shown]

AED=antiepileptic drug; bid=twice daily; BRV=brivaracetam; EEG=electroencephalogram; ENS=electroencephalographic neonatal seizures; ICF=Informed Consent form; iv=intravenous; LEV=levetiracetam; LDC=lidocaine; MDZ=midazolam; PB=phenobarbital; PHT=phenytoin

Note: The Screening Period is from signing and dating of the written ICF up to initiation of the first BRV dose.

^a BRV to be administered in addition to another AED.

[figure not shown]
Figure 5–3: Schematic overview of the study (Confirmatory Cohorts)

BRV=brivaracetam; PNA=postnatal age

¹ BRV Extension Period up to a PNA of 90 days is only applicable if subjects can intermittently not transition to a long-term study.

Figure 5–4: Screening and Evaluation Periods (Confirmatory Cohorts)

AED=antiepileptic drug; BRV=brivaracetam; EEG=electroencephalogram; ENS=electroencephalographic neonatal seizure; LEV=levetiracetam; LDC=lidocaine; MDZ=midazolam; PB=phenobarbital; PHT=phenytoin

^a Concomitant treatment with AEDs is permitted to continue in parallel with BRV treatment if subjects are on a stable dose from 1 hour prior to initiation of BRV treatment. Changes to concomitant AEDs are permitted from 3 hours onward following first BRV administration).

^b Duration of the Baseline EEG depending on seizure activity:

- for subjects with intermittent ENS: 1 hour
- for subjects in status epilepticus: up to 30 minutes

5.4 Rationale for study design and selection of dose

5.4.1 Rationale for study design

The current accepted medical practice (ie, standard of care) for neonatal seizures is initial treatment with PB with rapid progression to treatment with MDZ for patients without adequate seizure control after 2 doses of PB. In more than 50% of subjects, seizures are not controlled after first-line treatment with PB or other AEDs, and subsequent treatment with additional AEDs does not significantly improve seizure control (van Rooij et al, 2013b; Castro Conde et al, 2005; Boylan et al, 2004; Painter et al, 1999). Thus, study N01349 was designed for a flexible treatment of ENS, and only those subjects who do not have adequate seizure control with previous AED treatment will be permitted to continue in the study.

As the patient population of neonates with ENS is limited, the 2-step design of this study will allow confirmation (or adjustment) of dosing based on results from the first step (Exploratory Cohort) and evaluation of BRV efficacy in the second step (Confirmatory Cohorts). This adaptive design allows confirmation of dose and collection of PK, safety, and efficacy data, thereby potentially providing rapid access to alternative treatment in neonates.

The frequency, voltage, and morphology of the discharges may change within an individual seizure and between seizures in an individual neonate. At enrollment, subjects must be at least 34 weeks of CGA. In addition, term neonates up to 27 days of PNA and preterm neonates up to 40 weeks of CGA and 27 days of PNA can be enrolled. Neonates undergoing hypothermia treatment (eg, for the treatment of HIE) will also be enrolled.

Although newer AEDs are efficacious for the treatment of seizures in adults and older children, limited progress has been made in the treatment of neonatal seizures (Pressler et al, 2015; Pressler and Mangum 2013; Tulloch et al, 2012). Thus, clinical studies to assess the efficacy and safety of new treatment options in neonates are warranted.

5.4.2 Rationale for dose selection

The doses planned to be applied in this study are based on pediatric data collected in N01263 subjects (overall 96 subjects in the age range of 1 month to 17 years with the following number of subjects per pediatric age group: 1 month to <2 years of age, 29 subjects; 2 years to <6 years of age, 26 subjects; 6 years to <12 years of age, 24 subjects; 12 years to <16 years of age, 17 subjects). A physiological-based PK model was used to extrapolate the PK of BRV from older children. It is estimated that a dose of BRV 0.5mg/kg bid, administered to neonatal subjects, should yield the same BRV exposure range in plasma as observed in older children receiving the same dose on a mg/kg body weight basis. In adults, a similar exposure is achieved with a dose of 25mg bid, which represents the lowest dose approved for adults. A dose of 2mg/kg bid should result in similar exposure in neonates as compared to adults receiving 100mg bid (the highest approved dose in adults). Given the uncertainties of the extrapolation, as well as the variability and rapid changes in neonatal physiology, these predictions may or may not be precise; however, large discrepancies are not expected.

Based on the extrapolation explained above, subjects who enter the Exploratory Cohort will receive an initial low dose of BRV (0.5mg/kg [bid]). A starting dose of BRV 0.5mg/kg was selected because this dose offers a wide safety margin (4-fold) with respect to the highest BRV dose administered and tolerated in older children and adults with epilepsy. Simultaneously, a

dose of BRV 0.5mg/kg is potentially therapeutically beneficial to subjects in this study. In adjunctive treatment studies, a dosage of BRV 25mg bid is effective for POS in adult subjects with epilepsy.

For subjects who enter the Confirmatory Cohorts, the dosing frequency of BRV will be determined based on the PK findings of the Exploratory Cohort (see Section 5.1). The dose of BRV to be administered in the Confirmatory Cohorts will be determined by the evaluation of plasma samples collected in the Exploratory Cohort, as well as by the PK modeling of N01263 data described above, and should not exceed the range of plasma concentrations observed in children ≥ 1 month old who received BRV 4mg/kg/day. The plasma concentration of BRV 4mg/kg/day for neonates is predicted to be approximately equivalent to the plasma concentrations observed in adults who receive BRV 200mg/day. The dose in neonates to reach the same plasma concentrations will be confirmed or adapted upon completion of enrollment and analysis of PK and safety data from the Exploratory Cohort involving the DMC.

The BRV dose used in the Confirmatory Cohorts will be based on recommendations made by the DMC. Based on the DMC meeting held on 05 Nov 2020, the BRV dose and frequency selected for the Confirmatory Cohorts is 1mg/kg bid (2mg/kg/day). Based on data from the Confirmatory Cohorts, the BRV dose may be further adjusted in a staggered approach as determined by the DMC.

Furthermore, the posology of BRV for the Confirmatory Cohorts is proposed as an approximately 15-minute iv infusion in consideration of the following and is based on PK and safety data available from subjects ≥ 1 month old in N01263 and N01266:

BRV is well-tolerated orally up to 200mg/day in adult subjects with epilepsy and in children 1 month old to 16 years of age receiving up to 4mg/kg/day. In adults, a single iv infusion over 15 minutes or a bolus of BRV up to 150mg/day is well-tolerated. A dose of BRV 4mg/kg/day is predicted to be approximately equivalent to the highest BRV dosage (200mg/day) received by adults. In addition, iv BRV is bioequivalent to the same dose given orally in healthy adults when given as a bolus or as a 15-minute infusion.

Dose adjustment of BRV for the change in the formulation (switching from iv to oral solution) used during this study is not required as the AUC of BRV is bioequivalent between the following formulations: a tablet, a 15-minute iv infusion, and a bolus iv injection. In adults, iv BRV was administered to healthy volunteers, as well as subjects with epilepsy. Results showed that iv BRV was well-tolerated at all doses, up to 150mg per iv injection. Furthermore, the dose of BRV oral solution is bioequivalent to BRV tablets; therefore, dose adjustment is not required when switching between these formulations.

6 SELECTION AND WITHDRAWAL OF SUBJECTS

6.1 Inclusion criteria

To be eligible to participate in this study, all of the following criteria must be met:

1. An Independent Ethics Committee (IEC)-approved written ICF is signed and dated by the parent(s) or legal representative(s).
- 2a. Confirmation on VEEG of ≥ 2 minutes of cumulative ENS or ≥ 3 identifiable ENS prior to entering the Evaluation Period (ENS is defined as a seizure lasting for at least 10 seconds on VEEG), despite receiving previous AED treatment for the treatment of electroencephalographic seizures.

The occurrence of ENS during an up to 1-hour period must be confirmed either by the local or central VEEG reader prior to drug administration. Preferably, the central VEEG reader should confirm the required ENS.

3. Subject is male or female and must be at least 34 weeks of CGA. In addition, term neonates up to 27 days of PNA and preterm neonates up to 40 weeks of CGA and 27 days of PNA can be enrolled.
4. Subject weighs at least 2.3kg at the time of enrollment.
5. Subjects with or without concomitant hypothermia treatment.

6.2 Exclusion criteria

Subjects are not permitted to be enrolled in the study if any of the following criteria are met:

- 1a. Subject receiving AED treatment other than PB, MDZ, PHT, LEV (≤ 60 mg/kg/day), or LDC for the treatment of seizures prior to or at the time of enrollment (Confirmatory Cohorts only).
2. Subject with seizures responding to any of the following: previous AED treatment immediately prior to BRV treatment, pyridoxine treatment, or correction of metabolic disturbances (hypoglycemia, hypomagnesemia, or hypocalcemia).
3. Subject requires extra corporeal membrane oxygenation.
4. Subject has seizures related to prenatal maternal drug use or drug withdrawal.
5. Subject has known severe disturbance of hemostasis, as assessed by the Investigator.
6. Subject has a poor prognosis for survival, as judged by the Investigator.
- 7a. Subject has 2x upper limit of normal (ULN) of any of the following: aspartate aminotransferase (AST), alanine aminotransferase (ALT), and alkaline phosphatase (ALP), with the following exception:

For subjects with perinatal asphyxia, elevation of AST, ALT or ALP < 5 x ULN is acceptable, if initial and peak elevation of liver function tests (LFTs) occurs within 5 days after birth, and the time course of LFT elevation is compatible with hepatic injury due to perinatal asphyxia.

The determination of ULN will be based on the subject's gestational age (GA) and the site's normal range values for the respective GA.8a. Subject has direct (conjugated) bilirubin levels $>2\text{mg/dL}$.

9. Subject requiring or expected to require phototherapy or exchange transfusion due to elevated bilirubin.
10. Subject with rapidly increasing bilirubin that may preclude the subject from inclusion in the study at the discretion of the Investigator.
11. Subject with a severe cardiac condition, including subject with a diagnosis or signs of long QT syndrome (LQTS), and subject with a family history of LQTS.

6.3 Withdrawal criteria

Parent(s) or legal representative(s) are free to withdraw the subject from the study at any time, without prejudice to continued care.

Subjects **must** be withdrawn from the study if any of the following occur:

1. The Sponsor or a regulatory agency requests withdrawal of the subject.
2. Parent(s) or legal representative(s) withdraw their consent for the subject to participate.
3. Subject is treated with prohibited concomitant medications as defined in this protocol.
- 4a. Subject has direct (conjugated) bilirubin levels $>2\text{mg/dL}$.
5. Subject requires phototherapy or exchange transfusion due to elevation of total bilirubin.
- 6a. Subject has AST, ALT or ALP values $3\times$ ULN, with the following exception:

For subjects with perinatal asphyxia, elevation of AST, ALT or ALP $<5\times$ ULN is acceptable for continuation in the study, if initial and peak elevation of LFTs occurs within 5 days after birth, and if the time course of LFT elevation is compatible with hepatic injury due to perinatal asphyxia (ie, peak LFT elevation within a few days after birth, and subsequent normalization until up to day 14 after birth).

In case AST, ALT or ALP elevation $\geq 5\times$ ULN occurs within 5 days after birth, study drug must be discontinued and LFTs retested within 24 hours. If AST, ALT and ALP are confirmed to be $<5\times$ ULN, the subject may restart study drug after consultation with and approval by the Medical Monitor.

The determination of ULN will be based on the subject's GA and the site's normal range values for the respective GA.

Subjects **may** be withdrawn from the study if any of the following events occur:

- 7a. Subject experiences prolongation of seizure duration, a worsening of seizure burden, or emergence of new seizure type considered by the Investigator to require intervention.
8. Investigator may withdraw subject due to any medical condition, based on clinical judgment and discretion.
- 9a. Subject has AST, ALT or ALP values between $>2\times$ and $\leq 3\times$ ULN, with the following exception:

For subjects with perinatal asphyxia, elevation of AST, ALT or ALP <5 x ULN is acceptable for continuation in the study, if initial and peak LFT elevation occurs within 5 days after birth, and if the time course of LFT elevation is compatible with hepatic injury due to perinatal asphyxia (ie, peak LFT elevation within a few days after birth, and subsequent normalization until up to day 14 after birth).

The determinations of ULN will be based on the subject's GA and the site's normal range values for the respective GA.

10. Subject has rapidly increasing total bilirubin without requiring or being expected to require phototherapy or exchange transfusion; the subject's withdrawal will be at the discretion of the Investigator.

Investigators should attempt to obtain information on subjects in the case of withdrawal. The Investigator should document his/her effort (date and summary of the phone call and copy of the written message in the source documents) to complete the final evaluation. All results of these evaluations and observations, together with a narrative description of the reason(s) for removing the subject, must be recorded in the source documents. The eCRF must document the primary reason for withdrawal.

Investigators should contact the Medical Monitor, whenever possible, to discuss the withdrawal of a subject in advance.

6.3.1 Potential drug-induced liver injury IMP discontinuation criteria

Subjects with potential drug-induced liver injury (PDILI) must be assessed to determine if the investigational medicinal product (IMP) must be discontinued. In addition, all concomitant medications that are not medically necessary should also be discontinued.

The PDILI criteria below require immediate and permanent discontinuation of IMP:

- Subject has direct (conjugated) bilirubin >2 mg/dL.
- Subject has AST, ALT or ALP values >3 x ULN, with the following exception:

For subjects with perinatal asphyxia, elevation of AST, ALT or ALP <5 x ULN is acceptable for continuation in the study, if initial and peak LFT elevation occurs within 5 days after birth, and if the time course of LFT elevation is compatible with hepatic injury due to perinatal asphyxia (ie, peak LFT elevation within few days after birth, and subsequent normalization until up to day 14 after birth).

In case AST, ALT or ALP elevation ≥ 5 x ULN occurs within 5 days after birth, study drug must be discontinued and LFTs retested within 24 hours. If AST, ALT and ALP are confirmed to be <5 x ULN, the subject may restart study drug after consultation with and approval by the Medical Monitor.

The determination of ULN will be based on the subject's GA and the site's normal range values for the respective GA.

- Subject requires or is expected to require phototherapy or exchange transfusion due to elevation of total bilirubin values.

Investigators should attempt to obtain information on subjects in the case of IMP discontinuation to complete the final evaluation. Subjects with PDILI should not be withdrawn from the study

until investigation and monitoring are complete. All results of these evaluations and observations, as well as the reason(s) for IMP discontinuation and subject withdrawal (if applicable), must be recorded in the source documents. The eCRF must document the primary reason for IMP discontinuation.

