As soon as subjects are considered to be in status epilepticus, steps required for the preparation of the initial BRV infusion can be initiated (eg, assignment of BRV kits through interactive response technology [IRT] and the dilution of BRV solution for iv infusion), even if the required EEG recording is not completed by that time.

Status epilepticus in neonates for the purpose of this study is defined as follows:

- 15 minutes of continuous or cumulative electrographic or electroclinical seizure within 30 minutes

The occurrence of ENS during the Baseline Period must be confirmed either by the local or central VEEG reader prior to BRV administration. Preferably, the central VEEG reader should confirm the required ENS. Video-EEGs that are acquired per standard of care prior to consenting and meet study-specific technical and quality requirements (eg, ability for immediate cloud-based central review) can be used as part of the Baseline assessment VEEG.

- Evaluation Period (96 hours): The first administration of BRV marks the starting point of the Evaluation Period. Subjects in the Confirmatory Cohorts will receive iv BRV 1mg/kg bid (2mg/kg/day), as recommended by the DMC on 05 Nov 2020 based on the results of the PK analysis of the Exploratory Cohort as well an existing PK model from N01263. The DMC will continue to monitor the PK and safety of the subjects and dosing may be adjusted as new data are available. If subjects do not benefit from BRV treatment after 96 hours of BRV administration, BRV administration will be stopped and replaced by another AED.

Following the first BRV infusion, 6 PK blood microsamples (60 μ L/sample) will be collected during the 96-hour Evaluation Period for each subject for the determination of plasma concentrations of BRV and its metabolites, as described in [Table 5–5](#). Blood for PK samples should be drawn from a line different to that of the BRV infusion.

The AED PK sample should be collected 3 hours after the start of the initial BRV administration. In addition, opportunistic blood samples for the PK analysis may be used at the Investigator's discretion at any time during the Evaluation Period (see [Section 9.1](#)).

At the end of the Evaluation Period, subjects who benefit from BRV treatment may enter the BRV Extension Period in accordance with the Investigator's opinion. Subjects not entering the BRV Extension Period will proceed to the Down-Titration Period.

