- BRV Extension Period (28 days [up to 90 days] of PNA): Subjects can proceed to the BRV Extension Period if they benefit from BRV treatment during the Evaluation Period, in accordance with the Investigator's opinion. All subjects who participate in the BRV Extension Period must be offered entry into the long-term study, if they meet the eligibility criteria. Subjects will participate in the BRV Extension Period until they reach a stable condition that will allow them to enter the long-term study, if epilepsy is confirmed.

The anticipated duration of the BRV Extension Period per subject is up to 28 (+7) days of PNA. Subjects who are not able to be dosed with BRV oral solution at a PNA of 28 days may continue in the BRV Extension Period for an additional 7 days; subjects who are not able to be switched to BRV oral solution by the end of the additional 7 days of the BRV Extension Period will not be eligible for enrollment in the long-term study.

In the event that a long-term study is temporarily not available, subjects are allowed to remain in the BRV Extension Period until they reach a PNA of up to 90 days. For those subjects, the assessments planned for Unscheduled Visits (see [Section 8.1.3.3](#)) will be conducted in intervals of approximately 30 days during the prolonged Extension Period. The treatment with BRV will be managed through IVRS. Before subjects can roll-over to the long-term study, they must have switched to BRV oral solution.

- Subjects must switch to BRV oral solution before entering the long-term study. The timepoint of the switch from iv to oral solution will be at the discretion of the Investigator.

During the BRV Extension Period, subjects may continue receiving the same BRV dose administered at the end of the Evaluation Period; the BRV dose should not be increased, but may be decreased at the discretion of the Investigator.

Down-Titration Period (up to 1 week): A Down-Titration Period of up to 1 week is recommended for subjects in the Confirmatory Cohorts who discontinue BRV treatment prior to completion of the Evaluation Period, who do not proceed to the BRV Extension Period, or start the BRV Extension Period but do not enter the long-term study. The Down-Titration steps and duration may be adjusted at the Investigator's discretion.

- Safety Follow-Up Period: Subjects will proceed to the Safety Follow-Up Period once they complete the Down-Titration Period. The visit will occur 30±3 days after the final administration of BRV.

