Rescue medication should be given if the following occurs:

- There is no improvement in seizure burden within the first 3 hours after administration of BRV.
- Seizure burden is unacceptable to the Investigator, in which case rescue medication can be given earlier at any time, but ideally not in the first 3 hours after the initial administration of BRV.

Subjects in the Confirmatory Cohorts are allowed to switch over from BRV to another AED (eg, MDZ or PHT), if needed. Subjects discontinuing BRV treatment during the Evaluation Period should start the Down-Titration Period while completing the Evaluation Period in parallel for the full 96 hours. In this case, subjects will complete all study assessments, except the collection of blood microsamples for the determination of BRV plasma concentrations. Ideally, changing or adding a new treatment should not occur during the first 3 hours after the initial administration of BRV. Subjects who are switched from BRV to another AED will not be eligible to participate either in the BRV Extension Period or the long-term study.

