11.2.1 Evaluation of PDILI

The PDILI IMP discontinuation criteria (Food and Drug Administration [FDA], Guidance for Industry, Drug-induced liver injury, 2009) for this study are provided in Section 6.3.1, with the accompanying required follow-up investigation and monitoring detailed below. All PDILI events must be reported as an AE and reported to the study site and Sponsor within 24 hours of learning of their occurrence. Any PDILI event that leads to discontinuation must be reported as an AE of special interest (see Section 11.1.1.3) and must also be reported as an SAE see Section 11.1.1.2).

Evaluation of PDILI consists of the diagnostic testing and continued monitoring included in Table 11–3 specific tests dependent on laboratory results and corresponding symptoms) and consultation with a local hepatologist (if applicable; discussed in Section 11.2.1.1). Additional investigation and monitoring may be required and adapted based on the diagnosis after the cause of the liver injury/abnormality is confirmed (details in Section 11.2.1.4).

The results of all monitoring, including laboratory testing and other testing, should be made available to the study site and Sponsor.

All initial tests resulting in abnormal hepatic laboratory values need to be repeated, but appropriate medical action must not be delayed while waiting for the repeat result.

Table 11–3 summarizes the required investigations and follow-up for PDILI.

This document cannot be used to support any marketing authorization application and any extension or variation thereof.
PUBLIC COPY

Table 11–3: Required investigations and follow-up for PDILI

Patient population	Laboratory value		Immediate		Follow-Up	
	ALT/ AST/ALP	Direct (conjugated) bilirubin ^a	Consultation requirements	Actions	Testing	Evaluation
Subjects without perinatal asphyxia	≥3xULN according to the subject's GA and site's normal value	NA	Hepatology consultation (see Section 11.2.1); Medical Monitor must be notified within 24 hours (eg, laboratory alert) and subject discussed with Medical Monitor ASAP ^b	Immediate, permanent IMP discontinuation.	Essential: Must have repeat liver chemistry values and additional testing completed ASAP (see Section 11.2.1.1); recommended to occur at the site with HCP.	Monitoring of liver chemistry values at least twice per week until values normalize, stabilize, or return to within Baseline values.
Subjects with perinatal asphyxia ^c	≥5xULN according to the subject's GA and site's normal value	NA				

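### Confirmatory Cohorts: the liver stopping rule ends BRV for good, but general early-stop text leads to a BRV taper with no liver exception; separately, the withdrawal/rebound table omits the time after the last dose

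*Protocol*

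**What the plan says.** **Liver rule.** Protocol 6.3.1 states: "The PDILI criteria below require immediate and permanent discontinuation of IMP". The triggers are direct bilirubin above 2 mg/dL, AST, ALT or ALP above 3 times ULN, and actual or expected need for phototherapy or exchange transfusion because of bilirubin. Table 11-3 repeats the action, "Immediate, permanent IMP discontinuation", and adds that the "Medical Monitor must be notified within 24 hours". In perinatal asphyxia, values below 5 times ULN are tolerated if their time course fits. At 5 times ULN or more within 5 days of birth, BRV stops, the tests are repeated within 24 hours, and BRV may restart with Medical Monitor approval if they are back below 5 times ULN.

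**Taper text, Confirmatory Cohorts.** Section 5.1.2 says: "Subjects not entering the BRV Extension Period will proceed to the Down-Titration Period". On stops before the 96 hours are over, it says: "A Down-Titration Period of up to 1 week is recommended for subjects in the Confirmatory Cohorts who discontinue BRV treatment prior to completion". Later it adds: "Subjects discontinuing BRV treatment during the Evaluation Period should start the Down-Titration Period while completing the Evaluation Period in parallel". Section 8.2.2 gives the same direction to any baby who has received fewer than 8 doses. Related text stands in 8.2.3, 8.2.3.2, Table 5-2 footnote c and Table 5-3 footnotes a and g.

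**SAP.** Section 3.2.2.2.5 ends Down-Titration at the last BRV administration. Section 3.2.2.6 has Confirmatory babies enter Safety Follow-Up on completing Down-Titration. Section 10.4.11 describes withdrawal and rebound as adverse events after BRV has ceased, then plans summaries of TEAEs with onset during Down-Titration.

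**The concern.** A liver stopping rule in newborns has to work at the bedside, often from the schedule tables and the visit section. Staff who work from 8.2.2 or the footnotes for a baby stopped early are pointed to a period in which BRV is given. Staff who work from 6.3.1 are told to give no more. At stake is further exposure to a drug suspected of injuring the liver.

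Two analysis questions sit beside this. A Confirmatory baby who correctly gets no taper has no defined start of Safety Follow-Up. And for all Confirmatory babies, the table meant to show withdrawal and rebound covers a period that ends when BRV ends.

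**Working it through.** The protocol gives no figure to reproduce. The check compares passages, with a little arithmetic at the end.

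**1. Does Down-Titration mean more BRV?** Yes, on three counts. Protocol 8.2.4 lists BRV administration among its procedures, 5.1.3 counts it as up to 1 week of BRV exposure, and SAP 3.2.2.2.5 ends it at the last BRV dose.

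**2. Who is sent there, and how firmly?**
- *Any reason:* 8.2.2, for fewer than 8 doses.
- *Stop during the Evaluation Period, but in a narrower setting:* the last paragraph of 5.1.2 (switch to another AED), Table 5-2 footnote c (no benefit), and Table 5-3 footnote a (timing of a taper it has just called recommended).
- *End of Evaluation, or Extension Period Visit 2:* 5.1.2 (Evaluation Period), 8.2.3, 8.2.3.2 and Table 5-3 footnote g.
- *Recommendation only:* 5.1.2 (Down-Titration Period), 8.2.4 and Table 5-3 footnote a; 5.1.2 and 8.2.4 leave steps and duration to the Investigator.

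None of these carries a liver exception.

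**3. Does the liver text settle it?** Sections 6.3, 6.3.1, 11.2.1 to 11.2.1.4 and Table 11-3 do not mention Down-Titration. No passage states precedence.

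**4. Example.** Up to 8 doses in 96 hours is one every 96 / 8 = 12 hours. Safety laboratory tests are due at 24 hours, when a baby has had 2 doses (0 and 12 h), or 3 if the 24 h dose has been given. Take a baby without asphyxia whose ALT is then above 3 times ULN. Under 6.3.1 there are no further doses. Under 8.2.2, 2 or 3 is fewer than 8, so Down-Titration starts. The extra BRV cannot be quantified, because no taper steps are given; only the 1-week limit is stated.

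**5. Is there another route?** Table 5-3 footnote b opens Safety Follow-Up to babies who withdraw or do not enter the Extension. For the second group, 5.1.2 instead says "Subjects not entering the BRV Extension Period will proceed to the Down-Titration Period". As for withdrawal, 6.3 makes these liver findings must-withdraw criteria (for example, "Subject requires phototherapy or exchange transfusion due to elevation of total bilirubin"), but 6.3.1 says "Subjects with PDILI should not be withdrawn from the study" until investigation and monitoring are complete. The route exists but is deferred.

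**6. Safety Follow-Up start.** SAP 3.2.2.1.4 starts it after the last BRV administration in the Exploratory Cohort. SAP 3.2.2.6 ties entry to completing Down-Titration, so no start is defined for a Confirmatory baby with no taper. The visit date is unaffected: it is 30 ± 3 days after the last dose either way.

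**7. Withdrawal/rebound table.** From last dose to Safety Follow-Up visit: 30 − 3 = 27 to 30 + 3 = 33 days. Down-Titration ends at the last dose, so the 10.4.11 summaries cover 0 of those days. This holds with or without a taper.

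**8. Are these events lost?** No. SAP 10.2 counts every event with onset from the first BRV dose as a TEAE, and 10.2.1 includes an entire-study table. Only their place in the by-period tables is uncertain, for no-taper babies, because of step 6.

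**The case against.** The best reply is that ordinary reading resolves the conflict. Section 6.3.1 is specific and mandatory. Most early-stop taper text is advisory, with adjustable steps, and several of the sentences concern AED switches, lack of benefit or Extension Period Visit 2, which is scheduled for the day of entry to the long-term study. The Medical Monitor hears of every case within 24 hours. Deferring study withdrawal for the work-up does not authorise BRV in the meantime.

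Most of this stands, and it limits the point. A reader might infer that the protocol orders a taper after a liver stop, or that a site cannot comply with 6.3.1. The documents support neither. Nor is every taper sentence a separate contradiction; only 8.2.2 is both free-standing and independent of the reason. It would also be wrong to say that 6.3.1 always means no further BRV, given the asphyxia restart route.

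What remains is that 8.2.2 covers a liver stop by its terms, adjustable steps are not the same as no doses, and with 12-hourly dosing two dose times can fall within the 24-hour notice window. A liver rule should not depend on staff inferring which section wins.

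It is also fair to object that the 10.4.11 gap has nothing to do with liver stops. That is right: it is a separate point, affecting all Confirmatory babies.

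**Conclusion.** The point holds as an unresolved conflict in safety instructions and should be fixed. It concerns the Confirmatory Cohorts only (at least 36 babies). The number with a liver stop is not given; that it is small is an assumption. The text supports a risk that staff read the schedule before 6.3.1, not a prediction that babies will be tapered.

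The missing Safety Follow-Up start is a small consequence for babies without a taper. The 10.4.11 mismatch is independent and general: the table omits the post-cessation time that its own definition describes. A reader might infer that safety events go unreported, but the entire-study TEAE table keeps them. No effect on the primary PK variable, the responder rate or the sample size is shown.

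**What to change.** **Protocol.** State in 8.2.4 that subjects permanently discontinued under 6.3.1 receive no down-titration BRV, complete the remaining non-dosing assessments and go to Safety Follow-Up, and that the asphyxia restart route is unchanged. Cross-refer to this at least from 8.2.2 and the Table 5-2 and 5-3 footnotes.

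**SAP 3.2.2.6.** When there is no taper, start Confirmatory Safety Follow-Up after the last BRV dose, or after 96 hours if later.

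**SAP 10.4.11.** For all Confirmatory babies, add events with onset after the last BRV dose, through Safety Follow-Up, to the withdrawal/rebound summary.

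**Cost.** One protocol statement, a few cross-references and two SAP edits; no new type of data. The abrupt stop is already what 6.3.1 requires. Babies without a taper fall outside the Down-Titration seizure-freedom analysis, which SAP 4.6 limits to those who enter that period. There is slightly more tabulation, and background post-treatment events will appear in the withdrawal/rebound table, so it will need to be read with that in mind.
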